11.2 Grading of an Adverse Event

We will use the CTCAE as a reference for grading adverse events

11.3 Relatedness of Adverse Event to TDF

In this study, the relationship between an AE and TDF will be reported as one of the following:

- Not related
- Unlikely related
- Possibly related
- Probably related or
- Definitely related.

11.4 Serious Adverse Event Recording

All adverse events are recorded in the CRF. A serious adverse event (SAE) occurring to a subject should be reported to the EC that gave a favorable opinion of the study where in the opinion of the Chief Investigator the event was ‘related’ (resulted from administration of any of the research procedures) and ‘unexpected’ in relation to those procedures. Reports of related and unexpected SAEs should be submitted within 5 working days of the Chief Investigator becoming aware of the event, using the SAE form.

11.5 Subject Management of Adverse Events

All AEs will be treated as clinically indicated, and if concomitant treatment is given this will be recorded on the Concomitant Medication CRF. If necessary, participants will be referred for specialist care/advice.

The subject will be followed and treated by the research team until the clinical or laboratory AE has resolved or stabilised. The physician should perform any tests that are clinically indicated.

11.6 Serious Adverse Events

A serious adverse event is any untoward medical occurrence that:

- results in death
- is life-threatening
- requires inpatient hospitalization or prolongation of existing hospitalization
- results in persistent or significant disability/incapacity
- consists of a congenital anomaly or birth defect.

Other ‘important medical events’ may also be considered serious if they jeopardize the subject or require an intervention to prevent one of the above consequences.

11.7 Reporting of Serious Adverse Events

In this protocol, reporting means that SAEs must be reported by email by the study physicians to the study co-PI ([contact], [name]) within 24 hours of awareness using the SAE report form. The study co-PI ([name]) will be responsible for reporting the SAEs to the Ethics Committee per required timeline.

11.8 Safety Review of the Laboratory Report

All laboratory data will be reviewed by the team physicians to determine if kidney failure or a laboratory AE is present. The physicians or the co-PI will sign the laboratory report to confirm the report has been seen. Safety information will be reviewed on a regular basis.

12. Statistics

12.1 The Number of Participants

As this is a descriptive study of the PK, the sample size of 24 participants, who generate 60 dense PK curves, is assumed to describe the PK profile adequately and generate robust parameter estimates with reasonable precision.

12.2 Study endpoints

12.2.1 Primary endpoint

The primary endpoint is the Dense TDF concentration for 24 participants repeated at 3 gestational periods (2nd and 3rd trimester of pregnancy and 1 month post-partum). The end of the study is the date of the last visit to the clinic by a study subject which is anticipated as when the last infant involved in the study reaches 6 months of age.

12.2.2 Secondary endpoints

These are:

- Infant drug exposure comparing TDF concentrations in breastmilk samples, infant plasma and maternal plasma.
- Presence or absence of HBV DNA in maternal blood and breastmilk particularly after TDF cessation

- Proportion of infants that are positive for HBsAg and HBV DNA at birth (using cord blood), and HBsAg 2 month of age

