Primary	To measure the dense PK parameters of TFV in a steady-state during three gestational periods in TDF treated HBV mono infection	PK parameter profiles in maternal blood
Secondary	1. To investigate the TFV concentration , breastmilk and infants	- Maternal breastmilk TFV concentrations - Milk to maternal plasma concentration ratios (M/P) - Infant plasma drug concentration
	2. To investigate if/when HBV DNA is detected in blood and breastmilk after cessation of TDF.	HBV DNA in blood and breastmilk

2. Introduction – Background and Prior Research

Hepatitis B virus (HBV) can be asymptomatic for years but can also lead to chronic disease, cancer and hepatitis, hepatocellular carcinoma, and liver failure be eradicated with the current therapy. (1-3) Chronic maternal Hepatitis B virus (HBV) infection is an important source of perinatal transmission in regions of high HBV prevalence. In antenatal clinics at Shoklo Malaria Research Unit (SMRU), the Hepatitis B (HB) surface antigen (sAg) prevalence is 8.3% with a HB e-antigen (HBeAg) prevalence of 32.7% in those positive for HBsAg in 2012-2014.(4) Perinatal infection occurs in 70–90% of women with HBeAg positive chronic HBV compared with 0–30% in those with HBeAg negative chronic HBV (inactive carriers).(1) These infection rates reflect, in part, the failure of maternal and child health programs to prevent perinatal transmission with hepatitis B immunoglobulin (HBIG) and HB vaccines. Prevention of mother to child transmission (PMTCT) fails in an estimated 8–32% of cases with adequate preventive techniques.(5, 6) Antiretrovirals (ARVs), like Tenofovir Disoproxil Fumarate (TDF) are active against HBV and may reduce the risk of HBV transmission at birth if offered at the right time in pregnancy.(7-9)

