Primary Objective To measure the dense PK parameters of TFV in a steady-state during three gestational periods in TDF treated HBV mono infection	PK parameter profiles in maternal blood	Blood sampling every month and dense sampling every gestational period
Secondary Objectives To investigate the TFV concentration , breastmilk and infants To investigate if/when HBV DNA is detected in blood and breastmilk after cessation of TDF.	
 - Maternal breastmilk TFV concentrations - Milk to maternal plasma concentration ratios (M/P) - Infant plasma drug concentration HBV DNA in blood and breastmilk	At delivery and 1 month post-partum Post-partum monthly maternal blood and breastmilk samples up to 6 months.

5. Study Design

Participants with HBV mono infection and a measurable HBV DNA viral load attending SMRU antenatal clinics (ANC) on the Myanmar-Thailand border will be invited if they have a gestational age of at least 20 weeks. A total of 24 women: 12 participants enrolled in 2nd trimester (EGA ≥ 20 -<24 weeks) and 12 enrolled in 3rd trimester (EGA ≥ 28 -<36) with complete samples are required.

Women, identified by routine antenatal care screening for HBV will be invited to participate if they are HBsAg positive and meet the inclusion and exclusion criteria. Participants will be provided TDF 300mg daily and will continue TDF treatment until one month after delivery. The TFV concentrations will be measured monthly before delivery, at delivery, in cord blood and 1 and 2 months postpartum. Additional dense PK blood sampling will be done in the second and third trimester and postpartum. Breast milk samples timed with mother blood and infant blood samples will be included to measure drug concentrations in breastmilk as possible presence of HBV DNA viral in breastmilk following cessation of TDF.

The dense sampling for pharmacokinetics assessments will occur at least after 2 weeks of TDF treatment in second trimester between 22–26 weeks gestation, in third trimester between 30–38 weeks gestation, and 4 weeks postpartum. The dense sampling will entail twelve blood samples in a 24 hour period (24ml of blood in total). Women will be counseled about the importance of adherence. Direct Observed Treatment (DOT) in the 3 days prior to the dense blood sampling will be performed. The woman can choose to be admitted for these days or if a home visitor lives close enough be supervised at home.

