7.3 Study Evaluation

7.3.1 Screening Visit, Day -7

At screening visits, the subjects who are tested HBV infected and have a viable singleton pregnancy will be required to undergo the following tests and procedures:

- Obtain informed consent

- Obtain blood samples for laboratory tests; biochemistry (creatinine, phosphate, ALT), HBsAg, and HBeAg tests (and HBV DNA qualitative test if the mother is HBeAg negative)

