7.3.3 TDF administration

Generic GPO-TDF 300mg tablet will be used for this study. TDF 300mg will be administered daily and continue until 28 days post-partum.

The subject will be counseled about the importance of adherence. For the dense PK sampling it is of great importance to be in a steady state (see 7.3.5.1 “Pharmacokinetic Evaluation). To ensure this, we will perform DOT in the 3 days prior to the dense blood sampling. The subject can choose to be admitted for DOT administration (see 8.2.4 “Blood tests”)

Adherence survey and pill count will be performed monthly when the subject returns to the clinic to ensure compliance of TDF.

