8.2.1. Mother blood sample collections

A 6 ml venipuncture sample of whole blood will be collected at baseline and during monthly follow up (Table 1). Three mL will be placed in EDTA, plasma separated, and stored in 2 separate Eppendorf tubes for later testing of HBV DNA concentration. Another 3 ml will be placed in a plain tube, serum separated and (HBsAg, HBeAg at baseline) ALT, creatinine, and serum phosphate will be measured. HBV DNA and TDF concentrations will be determined. Any leftover serum will be stored frozen at -80°C.

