8.2.4 Breastmilk sample collection

At each sample time, staff and the participant will assess if she has adequate breast milk to collect a sample without adverse effect to the baby (eg. insufficient nutrition) or herself (eg. excessive squeezing). Participants will have the option to obtain breast milk by manual expression or using a (electronic) pump. If the woman has a cracked or bleeding nipples, this will be noted and appropriate care will be provided for the woman. If possible, milk for measurement of viral load will be collected from an intact nipple.

A. Colostrum (Viral load):

When the woman begins to have adequate colostrum production postpartum (day 1-2 on average), she will be asked to express 3 ml of colostrum into a sterile container. The woman may express from either or both breasts. Use of a breast pump will be allowed but hand expression is expected to be most effective.

B. 1 month breast milk (PK and viral load):

At hour 4 post-dose the mother will be asked to express the entire contents of one breast (choose the more full breast) into one clean container. The breast milk will be measured, mixed and a minimum of 10 ml aliquot taken. Remaining milk will be given to the mother to feed back to her infant with spoon, cup, or syringe, according to her preference. Infant feeding will be allowed to continue on demand (as is the cultural norm and recommended by the WHO) between the drug dose and the breast milk sample, and exposure to the infant will be considered essentially continuous.

C. 2-6 month breast milk (viral load):

At a convenient time during the visit, the mother will be asked to express a minimum of 5 ml into one clean container.

Table 1. Sampling schedule

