12.3 Data Analysis

Data cleaning will be performed prior to analysis to identify incomplete and incorrect data. All women will be censored at delivery for the analysis. Detailed statistical methods are described below.

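### Section 12.3 censors all women at delivery, which contradicts the plan's own post-partum PK, milk and HBV DNA analyses

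*Combined protocol and SAP*

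**What the plan says.** The opening paragraph of section 12.3, ahead of the specific methods in 12.3.1 to 12.3.3, states: "All women will be censored at delivery for the analysis". It does not say which analysis is meant and makes no exception.

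Other sections set out analyses that depend on data from after delivery:

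- **12.2.1, primary endpoint:** dense drug concentrations in the second trimester, the third trimester and 1 month post-partum.
- **12.3.2, PK analysis:** all samples are pooled in a mixed-effects model, with particular attention to differences between pregnancy and the post-partum period.
- **12.3.3, infant exposure:** a milk/plasma ratio from paired samples four hours post-dose. Section 8.2.4 (Breastmilk sample collection) places that milk sample at 1 month.
- **Synopsis and section 4, second secondary objective:** "To investigate if/when HBV DNA is detected in blood and breastmilk after cessation of TDF", with timing given in section 4 as "Post-partum monthly maternal blood and breastmilk samples up to 6 months". Section 12.2.2 turns this into the endpoint "Presence or absence of HBV DNA in maternal blood and breastmilk particularly after TDF cessation".

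On when treatment stops, section 7.3.3 says "TDF 300mg will be administered daily and continue until 28 days post-partum".

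**The concern.** Censoring at delivery means that nothing observed in a woman after delivery enters the analysis. Because treatment itself continues for 28 days after delivery, every sample taken after cessation lies beyond that cut-off. The sentence therefore cannot stand alongside the secondary objective on HBV DNA after cessation. The conflict with the primary endpoint is more serious, since one of its three sampling periods is post-partum and the comparison in 12.3.2 needs that period.

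An analyst working from the plan must either follow the sentence and lose these results, or depart from it with no written basis for doing so. Either course is awkward to defend once the data are in hand.

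**Working it through.** **Inputs**

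- 24 women, 12 enrolled in the second trimester and 12 in the third (Synopsis; section 5).
- 60 dense PK curves (12.1).
- Dense sampling in the second trimester only for women enrolled by then, in the third trimester, and at 4 weeks post-partum (8.2.4, Blood tests).
- One further single PK sample at 2 months post-partum (7.3.5.3).
- HBV DNA in maternal blood and milk at each post-partum month from 1 to 6 (7.3.5.3; Appendix C), plus colostrum at about day 1 to 2 (8.2.4, Breastmilk sample collection).
- TDF to 28 days post-partum (7.3.3).

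Complete sampling of all 24 women is assumed, so the counts are maxima.

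**Step 1: reproduce the plan's own figure.** Women enrolled in the second trimester give three curves and those enrolled in the third give two: 12 × 3 + 12 × 2 = 36 + 24 = 60. This matches 12.1.

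**Step 2: dense curves left if women are censored at delivery.** Curves from pregnancy: 12 × 2 + 12 × 1 = 36. Curves lost: 60 − 36 = 24, and 24/60 = 40%. These are all of the post-partum curves.

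**Step 3: HBV DNA after cessation.** Treatment ends at day 28, so the scheduled samples after cessation are those at months 2 to 6, which is five visits. Blood: 24 × 5 = 120. Milk: 24 × 5 = 120.

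**Step 4: all samples after delivery.** Blood for HBV DNA at months 1 to 6: 24 × 6 = 144. Milk at months 1 to 6 plus colostrum: 24 × 7 = 168.

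**Step 5: set planned against retained.**

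| Analysis | Planned | Left under literal censoring |
|---|---|---|
| Dense PK curves, all periods | 60 | 36 |
| Dense PK curves, post-partum | 24 | 0 |
| Single PK samples at 2 months | 24 | 0 |
| Milk/plasma pairs at 1 month | 24 | 0 |
| Blood HBV DNA, months 2–6 | 120 | 0 |
| Milk HBV DNA, months 2–6 | 120 | 0 |

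What survives is the pregnancy PK data and the maternal blood HBV DNA from pregnancy and delivery, taking the delivery sample itself as inside the cut-off. The 12.2.2 endpoint puts its emphasis on the period after cessation without being confined to it, so part of the blood endpoint would remain. The part that answers the stated objective would not.

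**The case against.** The strongest reply is that nobody would apply the sentence. The next sentence of 12.3 refers to detailed methods below it, and 12.3.2 and 12.3.3 cannot be carried out without post-partum data. Section 10.3 replaces women who withdraw because complete sample sets are needed, and the schedule in Appendix C runs to month 6. No maternal endpoint in 12.2 is a time to an event ending at delivery, so censoring has nothing to act on. All of this stands as evidence that the sentence is stray or lacks its intended scope. It does not correct the sentence, because no passage limits it.

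Four stronger readings are tempting, and the documents do not support them.

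- **That the study means to discard its post-partum data.** The endpoints, the methods and the sampling schedule all point the other way.
- **That presence or absence is a faulty endpoint.** It answers the stated objective, which asks whether and when HBV DNA is detected. It also records change in both directions: a woman detectable at 1 month who later becomes undetectable is captured, as is the reverse. What it misses is a rise or fall that stays above the assay limit.
- **That the lack of a reference visit or a rule for values below the limit is an error.** For a binary endpoint a value below detection counts as absent. Medians, which 12.3.1 allows, are unaffected by the value substituted when fewer than half the results are below the limit, and are reported as below the limit when more than half are.
- **That HBV DNA may be quantified only at the first and delivery visits, from one phrase in 8.2.4 (Blood tests).** The same section also speaks of monthly measurement, and Table 1, which may settle the matter, is missing from the text available here.

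Milk is collected only where supply allows (8.2.4, Breastmilk sample collection), so the milk counts may fall short even without censoring.

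**Conclusion.** The sentence is wrong as written. Taken literally, it removes all 24 post-partum dense curves out of 60 (40%), the 1-month milk/plasma ratio, and every HBV DNA value after cessation, up to 120 in blood and 120 in milk.

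The curve count follows from the plan's own numbers. The HBV DNA counts assume 24 women with complete samples at months 2 to 6. The conclusion needs no assumption about detection rates or variability. It is an internal contradiction affecting the primary endpoint and a secondary objective, and it can be cured before analysis.

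**What to change.** Delete the sentence in 12.3, or limit it to a named analysis of the pregnancy period. In either case add a statement that all post-partum PK, milk, infant and HBV DNA data are included in the analyses described in 12.2.1, 12.2.2, 12.3.2 and 12.3.3. This costs a wording amendment, with no new visits, samples or participants.

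**Optional, and not the correction of an error.** Quantified HBV DNA is already planned: section 8.2.1 has plasma "stored in 2 separate Eppendorf tubes for later testing of HBV DNA concentration", 8.2.4 (Blood tests) names a quantification assay, and 14.1 lists quantitative testing. The plan could therefore keep presence or absence and also describe log10 HBV DNA in maternal blood by visit, giving the number of values below the assay limit. That would show rises and falls that stay above the limit. The cost is a little more analysis work. Laboratory cost would rise only if the post-partum samples were meant to be tested qualitatively.

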12.3 Data Analysis

Data cleaning will be performed prior to analysis to identify incomplete and incorrect data. All women will be censored at delivery for the analysis. Detailed statistical methods are described below.

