12.3.2 Pharmacokinetic data

Densely collected TDF samples will be analysed using a model-independent approach (i.e. non-compartmental analysis) with the help of pharmacokineticist specialists (prof [name] and prof [name]). All collected samples will be pooled and analysed using nonlinear mixed-effects modelling to develop a detailed PK model that describes the concentration-time relationship and possible impact of clinical covariates, such as age and body weight. Particular focus will be on describing and quantifying potential PK differences during pregnancy (i.e. increasing gestational age) and compared to post-partum.

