12.3.3 Infant drug exposure

Infant exposure to TFV will be estimated using drug concentration in maternal plasma, maternal breast milk, and infant plasma. Milk/plasma ratio will be calculated using the paired breast milk and plasma concentrations at 4 hours after dosing. This may slightly overestimate the M/P ratio as determined by the ratio of the concentration AUC for breast milk and plasma, as hour 4 is expected to be the peak breast milk concentration, and plasma concentrations will be decreasing. This M/P ratio will be compared with published values from prior studies in women receiving using TDF in combination with other antivirals for treatment or prevention of HIV.

13 Human subjects considerations

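### Section 12.3 censors all women at delivery, which contradicts the post-partum data needed for the primary endpoint, the 60-curve count, the PK comparison and the milk analyses

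*Combined protocol and SAP*

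**What the plan says.** The general lead-in to section 12.3, placed before the detailed methods in 12.3.1 to 12.3.3, states: "All women will be censored at delivery for the analysis". No analysis is named.

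Other sections call for maternal data collected after delivery:

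- **12.2.1, primary endpoint:** dense concentrations in 24 participants, "repeated at 3 gestational periods (2nd and 3rd trimester of pregnancy and 1 month post-partum".
- **12.1, sample size:** justified by 24 participants "who generate 60 dense PK curves".
- **12.3.2, PK analysis:** "All collected samples will be pooled and analysed using nonlinear mixed-effects modelling", with particular focus on "describing and quantifying potential PK differences during pregnancy (i.e. increasing gestational age) and compared to post-partum".
- **12.3.3, infant exposure:** "Milk/plasma ratio will be calculated using the paired breast milk and plasma concentrations at 4 hours after dosing". The only 4-hour milk sample is the one listed in 8.2.4 (Breastmilk sample collection) as "1 month breast milk (PK and viral load"; 7.3.5.3 places it at the same visit.
- **12.2.2, secondary endpoint:** "Presence or absence of HBV DNA in maternal blood and breastmilk particularly after TDF cessation". Section 7.3.3 continues TDF until 28 days post-partum, so every sample taken after stopping is a post-delivery sample.

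**The concern.** Censoring normally belongs to a time-to-event analysis, and section 12 has none. In a concentration dataset the natural literal reading is that a woman contributes no data after delivery. On that reading the analyst drops one of the three periods that define the primary endpoint and cannot make the comparison with post-partum on which 12.3.2 places its focus.

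Two of the three listed secondary endpoints would also be largely lost: infant exposure through paired maternal milk and plasma, and HBV DNA in milk and after TDF is stopped. The third, infant infection status, survives at birth through cord blood. Its 2-month HBsAg part is unclear because the sentence censors women and says nothing of infants. The same doubt applies to infant plasma concentration at 1 month.

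An analyst who instead follows 12.3.2 and 12.3.3 keeps all of these data. The two readings give different datasets for the primary endpoint, and the choice between them could be made after the data are seen.

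**Working it through.** **Inputs**

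- 12 women enrolled in the second trimester (T2) and 12 in the third (T3): synopsis and section 5.
- Dense sampling in T2 (only for women enrolled then), in T3, and at 4 weeks post-partum: 8.2.4 (Blood tests) and 7.3.5.3.
- 12 samples per dense curve: section 5 and 7.3.5.1.1.
- One 4-hour milk sample per woman at 1 month, and one single TFV sample at 2 months: 7.3.5.3.
- Monthly maternal blood and milk for HBV DNA from month 1 to month 6: 7.3.5.3.
- No alpha, power, effect size or SD is given, so the check is a count.

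**Step 1. Reproduce the plan's own figure.** Curves = (T2 women × 3 periods) + (T3 women × 2 periods) = 12 × 3 + 12 × 2 = 36 + 24 = 60. This matches 12.1 exactly. By period: 12 in T2, 24 in T3 and 24 post-partum. (Taking 12.2.1 to mean all 24 women at all 3 periods gives 72, which is not the stated figure.)

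**Step 2. Apply the censoring rule.** Curves = 12 × 2 + 12 × 1 = 24 + 12 = 36. The loss is 60 − 36 = 24 curves, or 24/60 = 40%. It is the whole post-partum period, one curve per woman.

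**Step 3. Count what each reading keeps.**

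| Quantity | 12.3.2 and 12.3.3 govern | 12.3 read literally |
|---|---|---|
| Dense curves | 60 | 36 |
| Dense samples (× 12) | 720 | 432 (288 lost) |
| Possible within-woman T3 vs post-partum pairs | 24 | 0 |
| Possible within-woman T2 vs post-partum pairs | 12 | 0 |
| Possible within-woman T2 vs T3 pairs | 12 | 12 |
| Single TFV samples at 2 months | 24 | 0 |
| Milk/plasma pairs at 4 hours | up to 24 | 0 |
| Maternal blood HBV DNA, months 2 to 6 (5 × 24) | up to 120 | 0 |
| Milk HBV DNA, months 2 to 6 (5 × 24) | up to 120 | 0 |

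The pair counts show what the design could support; the plan does not prespecify a paired test. The literal reading would also remove colostrum, the month-1 HBV DNA samples and the post-partum ALT and creatinine values. Antenatal and delivery TFV, HBV DNA and biochemistry would remain, as would the cord-blood results.

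**Step 4. Look for text that limits the rule.** There is none. No section describes an analysis that ends at delivery, and the plan gives no order of precedence between the lead-in and the subsections.

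**The case against.** The strongest reply is that the intent is easy to recover. The same lead-in refers the reader to the detailed methods below it, and those methods, the primary endpoint and the curve count all require post-partum data. One sentence stands against the whole design, and it may be leftover text or refer only to pregnancy follow-up. Because nothing in the plan defines what censoring would do here, deleting every post-delivery sample is one reading and not the only one. No visit or sample depends on the sentence, the study is descriptive with no test to distort, and the problem can be corrected before analysis without losing data.

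Much of this is fair. Inclusion of post-partum data is very probably what was meant, and 40% is an upper bound, not an expected loss. But probable intent does not remove a written rule covering all women. An analyst who sets it aside departs from the plan on the primary dataset without authority in the text, and one who obeys it produces the wrong dataset. That the remedy is easy is a reason to apply it now.

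**Conclusion.** The contradiction is real and must be fixed before analysis. As written, 12.3 cannot be followed together with 12.1, 12.2.1, 12.2.2, 12.3.2 and 12.3.3. The size runs from no loss, if the detailed methods govern, to 24 of 60 dense curves (40%; 288 of 720 dense samples), if the lead-in governs. In the second case the comparison with post-partum, the milk/plasma ratio and the endpoint on HBV DNA after TDF is stopped would have no maternal data.

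The counts assume the planned 12 + 12 women with complete samples, full attendance at post-partum visits and enough milk at each one. The status of the infant outcomes under the rule is ambiguous and is not counted as a loss.

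**What to change.** Delete the sentence, or limit it to a named analysis; for example, state that gestational age as a model covariate stops accruing at delivery. Then add to 12.3:

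1. All dense profiles (T2, T3 and 1 month post-partum) enter the non-compartmental analysis.
2. All collected maternal TFV samples, including the single sample at 2 months post-partum, enter the mixed-effects model.
3. Maternal HBV DNA, milk and infant outcomes are analysed through their scheduled post-partum visits, up to 6 months.

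The cost is one sentence removed or narrowed and two or three added. No new participants, samples or visits are needed.
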